2.7.2.2 Analysis of uncorrected ACPR rate using Kaplan-Meier method

Analysis will be performed on the FAS and PPS.

If Cohort 2 does not stop early-

The proportion of patients with uncorrected ACPR at Day 29 and Day 43 and 95% CI will be estimated using the Kaplan-Meier method ([Stepniewska and White 2006](#) and [WHO 2015](#)) stratified by Cohort. For each cohort, an asymptotic two-sided 95% CI for the difference in proportion of responders between two treatment groups will be calculated from the z-test statistic distribution based on the variance of individual proportion using the Greenwood

formula (See [Section 2.5.4.1](#)). For pooled cohorts 1 and 2, an asymptotic two-sided 95% CI for the difference in proportion of responders between two treatment groups will be calculated.

If Cohort 2 stops early-

The proportion of patients with uncorrected ACPR at Day 29 and Day 43 and 95% CI will be estimated using the Kaplan-Meier method ([Stepniewska and White 2006](#) and [WHO 2015](#)) by Cohort except Cohort 1 along with an asymptotic two-sided 95% CI for the difference in proportion of responders between two treatment groups. For Cohort 1, an asymptotic two-sided 95% CI for each treatment group along with between treatment difference in proportion of responders will be calculated

Event = PCR-uncorrected non-responder during the study (same as at Day 15, Day 43, See [Section 2.1](#)). The event time is the first time when the patient becomes a non-responder without PCR-correction. If a patient parasite is not cleared at all, Day 7 is considered as the event time.

The uncorrected ACPR rate at Day 29 is estimated by the survivor function at Day 29.

Rule for censoring:

The following censoring rules will be applied to the patients who were not non-responders

- Patients who received non-rescue anti-malaria medication (i.e., receiving antimalaria treatment without reappearance of parasites) will be censored at the first time of anti-malaria medication.
- Other patients will be censored at the time of last parasitemia assessment.

Appendix Table 5-21 provides a comparison of treatment outcome assignments for both uncorrected and PCR-corrected ACPR in FAS and PPS for various specific scenarios.

2.7.2.3 Treatment failure related parameters

Following is the list of treatment failure related variables-

- proportion of patients with parasitaemia at 12, 24, and 48 hours after treatment
- proportion of patients with early treatment failure (ETF)
- proportion of patients with late clinical failure (LCF)
- proportion of patients with late parasitological failure (LPF)

The above parameters will be determined using the uncorrected asexual parasite counts.

In addition, patients whose outcome status cannot be determined due to incomplete/missing data will be excluded from analysis. Which means that the proportion of patients with an endpoint will be based upon the patients who experience treatment failure or have malaria blood film result at Day 43 for LCF and LPF.

For the above variables, proportion and confidence intervals will be calculated using the exact confidence interval as follows:

If Cohort 2 does not stop early, then 95% CIs will be provided for each treatment group by cohort. In addition, Cohorts 1 and 2 will be pooled together and 95%CI will be provided for each treatment group.

If Cohort 2 stops early, then 95% CIs will be provided for each treatment group by cohort except Cohort 1. For Cohort 1, 95% CI will be provided for each treatment group.

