### **Treatment failure related parameters:**

For the following parameters, 2-sided 95% confidence intervals will be provided for each treatment group using the Clopper-Pearson method by cohort and for Cohorts 1 and 2 pooled:

- proportion of patients with ETF
- proportion of patients with LCF
- proportion of patients with LPF

In addition, following analysis will be performed. 2-sided 95% confidence intervals for the difference between KAF156 and LUM-SDF combo and Coartem® will be provided for Cohorts 1 and 2 pooled using a Mantel-Haenszel estimate of the common risk difference stratified by cohort. 2-sided 95% confidence intervals for the difference between the 2 treatment groups for each Cohort will be constructed using the Wilson uncorrected method.

The above parameters will be determined using the uncorrected parasite counts. In addition, patients whose outcome status cannot be determined due to incomplete/missing data will be excluded from analysis.

At each visit, PCR uncorrected failure will be classified into initial infection not cleared, ETF, LCF before Day 8, recrudescence, new infection, negative PCR, missing PCR, or missing assessment. The reason will be tabulated using the FAS.

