2.1.1.1 Definition of treatment failures

Early Treatment Failures (ETF)

Patient will be classified as ETF upon meeting any of the following criterion

- Development of danger signs or severe malaria on Day 2, Day 3, Day 4 in the presence of parasitaemia.
- Parasitaemia on Day 3 higher than Day 1 count irrespective of axillary temperature.
- Parasitaemia on Day 4 with axillary temperature $\geq 37.5^{\circ}\text{C}$.
- Parasitaemia on Day 4 equals to or more than 25% of count on Day 1.

Late Clinical Failure (LCF)

Patient will be classified as LCF upon meeting any of the following criterion

- Development of danger signs or severe malaria on any day from Day 5 to Day 43 in the presence of parasitaemia without previously meeting any of the criteria of early treatment failure.
- Presence of parasitaemia and axillary temperature $\geq 37.5^{\circ}\text{C}$ on any day from Day 5 to Day 43 without previously meeting any of the criteria of Early Treatment Failure.
- Missing body temperature assessment in presence of parasitemia will be classified as LCF.

Late Parasitological Failure (LPF)

- Presence of parasitaemia on any day from Day 8 to Day 43 and axillary temperature $< 37.5^{\circ}\text{C}$ without previously meeting any of the criteria of Early Treatment Failure or Late Clinical Failure.

Note: If the temperature is measured using other routes, such as oral/tympanic/rectal, the corresponding threshold for fever is 38.0°C . Danger signs or severe malaria is recorded as adverse events. The adverse event start date of danger signs or severe malaria will be used in the determination of ETF and LCF. Only *P. Falciparum* asexual form is used for parasitaemia/parasite in the assessments of treatment failure and ACPR in [Section 2.1.1.2](#) below. The body temperature assessment closest to the blood smear assessment date will be used.

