2.7 Analysis of secondary efficacy objective(s)

2.7.1 Secondary efficacy endpoints

Secondary efficacy variables include:

1. PCR-corrected ACPR at Days 15, Day 29 (Run-in Cohort) and 43;
2. Uncorrected ACPR at Days 15, 29, and 43;
3. Proportion of patients with parasitaemia at 12, 24, and 48 hours after treatment;
4. Time to parasite clearance (PCT), defined as time from the first dose until the first total and continued disappearance of (*P. Falciparum*) asexual parasite forms which remained at least a further 48 hours;
5. Time to fever clearance (FCT), defined as time from the first dose until the first time the body temperature decreased below and remained below 37.5°C (axillary equivalent) for at least a further 24 hours;
6. Proportion of patients with early treatment failure (ETF);
7. Proportion of patients with late clinical failure (LCF);
8. Proportion of patients with late parasitological failure (LPF);
9. Incidence rate of recrudescence and new infection at Days 15, 29 and 43.

Analyses of ACPRs (PCR corrected or uncorrected) will be based on the FAS and PPS. Analyses of other secondary efficacy variables will be based on the FAS.

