2.7.2.1 PCR-corrected ACPR and uncorrected ACPR

Analysis will be performed on PPS and FAS.

If Cohort 2 does not stop early-

At each visit, the ACPR rate with 95% confidence intervals will be provided using Clopper-Pearson method for each treatment group by cohort. Two-sided 95% CI for the difference between two treatment groups will be provided using Wilson's uncorrected method by cohort. Two-sided 95% CI for the difference between two treatment groups will be provided for Cohorts 1 and 2 pooled using Mantel-Haenszel estimate of the common risk difference stratified by cohort (see SAS manual version 13.2 Pages 2681-2682, 2014).

If Cohort 2 stops early –

At each visit, the ACPR rate with 95% CIs will be provided using Clopper-Pearson method for each treatment group for Cohort 1 and 95% CIs for the Cohort 2; two-sided 95% CI for the difference between two treatment groups will be provided for Cohort 1 only using Wilson's uncorrected method. Handling of missing values/censoring/discontinuations

Data will be handled as follows for ACPRs (PCR corrected or uncorrected):

- For PCR-corrected ACPR, presence of parasitaemia which were determined to be new infection from Day 8 and before Day 29 are excluded from the PPS, however, new infections at Day 29 or after Day 29 but before Day 43 are included in the PPS. At Day 43, 2 analyses will be performed, these new infections are considered as non-responders in one analysis and as responders in another analysis. For FAS, similar 2 analyses will be performed, new infections prior to a visit will be considered non-responders in one analysis and as responders in another analysis.
- For the PCR-corrected ACPR, the patient who is not classified as PCR-corrected nonresponder at earlier timepoint, and the PCR data is missing will be excluded from the PPS based analysis; however, for FAS, the patient will be considered as non-responder from the day of test.
- New infection at a visit means no recrudescence at prior visits (e.g., new infection at Day 43 means no recrudescence).
- Missing/undetermined responses at a visit due to missing blood smear data at the visit will be counted as non-responders (PCR corrected or uncorrected) unless there is a later blood smear test indicating no parasitemia, for the FAS; however, such patients will be excluded from the PPS based analysis.

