Day 43/End of study	43	Day 34 and above	Day 30 and above	

Table 5-6 Analysis visit windows based on study day and time

Analysis Visit	Analysis timepoint	Analysis window for assessment group			
		Parasite count/Temperature*	ECG	PK (Run-in)	PK (Cohorts 1&2)
Baseline	0 hrs	up to 0 hrs	up to 0 hrs	up to 0 hrs	up to 0 hrs
Day 1	1 hrs	NA	NA	> 0 - 2 hrs	NA
	3 hrs	NA	>0 – 4.5 hrs	> 2 – 3.5 hrs	>0 – 4.5 hrs
	4 hrs	NA	NA	>3.5 – 4.5 hrs	NA
	5 hrs	NA	NA	>4.5 – 5.5 hrs	NA
	6 hrs	>0 - 9 hrs	>4.5 - 15 hrs	>5.5 - 7 hrs	>4.5 – 15 hrs
	8 hrs	NA	NA	>7 – 16 hrs	NA
	12 hrs	>9 - 18 hrs	NA	NA	NA
Day 2	24 hrs	>18 hrs to 33 hrs	>15 – 25.5 hrs	>16 – 24.5 hrs	>15 – 25.5 hrs
	25 hrs	NA	NA	>24.5 – 26 hrs	NA
	27 hrs	NA	>25.5 – 28.5 hrs	>26 - 27.5 hrs	>25.5 – 28.5 hrs
	28 hrs	NA	NA	>27.5 – 28.5 hrs	NA
	29 hrs	NA	NA	>28.5 – 29.5 hrs	NA
	30 hrs	NA	>28.5 - 39 hrs	>29.5 - 31 hrs	>28.5 – 39 hrs
	32 hrs	NA	NA	>31 - 40 hrs	NA
	36 hrs	>33 – 42 hrs	NA	NA	NA
Day 3	48 hrs	>42 – 60 hrs	>39 – 49.5 hrs	>40 – 60 hrs	>39 – 60 hrs
Day 4	51 hrs	NA	>49.5 - 52.5 hrs	NA	>49.5 - 52.5 hrs
	54 hrs	NA	>52.5 – 61 hrs	NA	>52.5 – 61 hrs
	68 hrs	NA	>61 – 70 hrs	NA	>61 – 70 hrs
	72 hrs	>60 hrs to Day 4	>70 hrs to Day 5	>60 – 120 hrs	> 60 hrs
Day 5	NA	Day 5 - 6	NA	NA	NA
Day 8	168 hrs	Day 7 – 11	Day 6 -25	>120 hrs	NA

Day 15	NA	Day 12 - 26	NA	NA	NA
Day 29	NA	Day 27 - 33	NA	NA	NA
Day 43/End of study	NA	Day 34 and above	Day 26 and above	NA	NA

*Temperature should be checked every 6 hours until no fever. Since temperature is used for treatment failure also, the same window of parasite count is used.

Table 5-7 Rules for flagging variables

Timing of measurement	Type of data	Rule
Baseline	All data	The last measurement made prior to administration of the first dose of study treatment – note this may include measurements taken on the day of randomization. If a patient did not receive any dose of study treatment, then the randomization date will be used.
Post-baseline efficacy	parasite count and temperature	The measurement closest to the target day/time will be used. In the event two measurements are taken equally apart, the first one will be used.

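### The LCF and LPF proportions use a denominator chosen partly by outcome, which modestly overstates late failure if loss to follow-up is independent of failure

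*SAP*

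**What the plan says.** SAP 2.7.1 lists the LCF and LPF proportions among the secondary efficacy variables. It gives both the FAS and the per-protocol set for the ACPR endpoints, then states: "Analyses of other secondary efficacy variables will be based on the FAS". Protocol 12.5.1 names the same set.

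Protocol 12.5.1 adds, for the failure parameters, that "patients whose outcome status cannot be determined due to incomplete/missing data will be excluded from analysis". SAP 2.7.2.3 repeats this and makes it operational: for LCF and LPF the proportion is "based upon the patients who experience treatment failure or have malaria blood film result at Day 43 for LCF and LPF". The estimator is a simple one: "proportion and confidence intervals will be calculated using the exact confidence interval".

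The failure window is long. SAP 2.1.1.1 defines LPF as "Presence of parasitaemia on any day from Day 8 to Day 43 and axillary temperature" below 37.5 °C, and LCF can occur from Day 5 to Day 43. In the visit-window tables of SAP 5.1.4, a parasite count belongs to the Day 43 visit if taken on "Day 34 and above"; the Day 29 window ends at Day 33.

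The SAP treats a child with no Day 43 film differently elsewhere. In the Kaplan-Meier analysis of uncorrected ACPR (2.7.2.2): "Other patients will be censored at the time of last parasitemia assessment". In the FAS analysis of ACPR (2.7.2.1): "Missing/undetermined responses at a visit due to missing blood smear data at the visit will be counted as non-responders", unless a later film is negative. For recrudescence and new infection (2.7.2.5, 2.7.2.6), such a child is censored.

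**The concern.** Staying in the denominator depends on the outcome. A child who fails at Day 15 and never returns is kept. A child who is parasite-free at Day 29 and has no film from Day 34 on is removed, although about four weeks of failure-free follow-up were observed. Observed failures never leave the calculation, but observed failure-free time does.

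Two things follow. First, the reported proportions tend to lie above the risk by Day 43 that they are meant to estimate. Second, LCF and LPF are components of uncorrected ACPR failure, yet the same lost child is censored or counted as a non-responder for the composite and deleted for the components. Incomplete follow-up will therefore enter the component and composite tables in different ways. No Kaplan-Meier or missing-data sensitivity analysis is planned for LCF or LPF: SAP Table 2-4 leaves the time-to-event column blank for both.

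**Working it through.** **Inputs.** The documents give no expected LCF or LPF rate, no loss-to-follow-up rate and no failure timing, so these are assumptions. Arm size comes from SAP 3.1.1 (protocol 12.8.1): 92 evaluable per group and 16% per-protocol exclusions give 92 / 0.84 = 109.5, so 110 per arm and 220 in total, as stated. The 16% serves below only as the high end of the assumed loss.

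**Bounds.** Let p be the true proportion with late failure by Day 43 and d the proportion lost, with loss independent of failure. ETF is ignored for simplicity. Let F be the proportion whose failure is observed before loss. Non-failures with a Day 43 film make up (1 − p)(1 − d). The rule reports

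R = F / [F + (1 − p)(1 − d)].

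- Failures seen before loss are kept, so F is at least p(1 − d). Then R ≥ p.
- F cannot exceed p. Then R ≤ p / [p + (1 − p)(1 − d)].

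Upper bounds for p = 20%: 0.20 / (0.20 + 0.72) = 21.7% at d = 10%, and 0.20 / (0.20 + 0.672) = 22.9% at d = 16%. For p = 30% they are 32.3% and 33.8%.

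**Where R falls between the bounds.** Assume failures split 5/15/40/40% over Days 8, 15, 29 and 43, with p = 20%.

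- *Loss spread evenly, d = 10%* (2.5, 5, 7.5 and 10% lost before the four visits). F = 0.20 × (0.05×0.975 + 0.15×0.95 + 0.40×0.925 + 0.40×0.90) = 0.18425. R = 0.18425 / (0.18425 + 0.72) = 20.4%.
- *All loss between Days 29 and 43, d = 10%.* F = 0.20 × (0.60 + 0.40×0.90) = 0.192. R = 0.192 / 0.912 = 21.1%.
- *All loss before Day 8, d = 10%.* F = 0.18. R = 0.18 / 0.90 = 20.0%.
- *Loss spread evenly, d = 16%.* F = 0.20 × (0.05×0.96 + 0.15×0.92 + 0.40×0.88 + 0.40×0.84) = 0.1748. R = 0.1748 / 0.8468 = 20.6%.

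With p = 20% and 110 children, the standard error is √(0.20×0.80/110) = 3.8 points. The excess at d = 10% is therefore 0 to 1.1 points, or at most about 0.3 standard errors.

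**Comparison of estimators, p = 20%, loss spread evenly**

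| Estimator | d = 10% | d = 16% |
|---|---|---|
| SAP 2.7.2.3 rule | 20.4% | 20.6% |
| Kaplan-Meier, censored at last film | 20.0% | 20.0% |
| Observed failures over the full FAS | 18.4% | 17.5% |

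**Components.** LCF and LPF are reported separately over the same denominator, so the relative inflation carries over and the points shrink. If one component accounts for 5 of the 20 points and has the same timing, d = 10% spread evenly gives 0.05×0.92125 / 0.90425 = 5.1%, with an upper bound of 0.05 / 0.92 = 5.4%.

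**When loss is not independent.** If a fraction e is excluded and would fail with probability q, the truth is (1 − e)R + e·q. The rule overstates when q < R and understates when q > R. In the even 10% case the excluded children would fail at (0.20 − 0.18425) / (1 − 0.90425) = 16.4%, below R = 20.4%.

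**The case against.** The exclusion is openly stated, and the protocol names the FAS and excludes undetermined patients in the same section. A reader might infer a hidden contradiction with the FAS; the documents do not support that. The SAP spells out the protocol's rule without calling the result a subset.

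A reader might also infer that every failure is counted and that only non-failures drop out. That is too strong. A child lost at Day 10 who would have failed at Day 29 leaves both numerator and denominator. Upward bias is therefore conditional: it vanishes if all loss precedes the first late failure, and it can reverse.

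Nor is p / [p + (1 − p)(1 − d)] the expected result. It is a ceiling that assumes no failure is missed through loss. The 16% is not a loss rate either: per-protocol exclusion also covers low dosing, antimalarial use, early new infection and protocol deviations. The open-ended Day 43 window limits how many children leave.

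It is tempting to infer a spurious treatment difference from unequal loss in an open-label trial. Protocol 12.5.1 does plan between-arm intervals, but SAP 2.7.2.3 plans intervals per arm only, and Table 2-4 marks no between-treatment comparison for these endpoints.

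Finally, the composite of failures is already covered by uncorrected ACPR, with Kaplan-Meier censoring and a missing-as-non-responder analysis, and the protocol tabulates missing assessments among the reasons for uncorrected failure. Exact agreement with ACPR should not be expected, since ACPR also counts non-clearance as non-response.

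All of this stands and limits the size of the point. It does not remove the outcome-dependent denominator, or the absence of a censored analysis for LCF and LPF separately.

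**Conclusion.** The point holds as a minor one. SAP 2.7.2.3 keeps every observed failure and drops children observed failure-free to Day 29 who have no film from Day 34 on. Under independent loss the proportions cannot be too low. With an assumed 20% late failure and 10% loss they come out about 0 to 1 point high, with the exact excess set by when loss falls. The direction is not guaranteed if lost children fail more often than those counted. SAP 2.7.2 calls the secondary endpoints supportive and sets no hypotheses for them. The primary analysis, ETF and parasitaemia at 12, 24 and 48 hours do not use the Day 43 condition.

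**What to change.** In SAP 2.7.2.3, replace the failure-or-Day-43-film denominator for LCF and LPF. Estimate the cumulative incidence of each by Day 43 in the FAS, with ETF, LCF and LPF as competing types of first failure and children without failure censored at the last film. This matches the censoring approach of 2.7.2.2 and 2.7.2.5. Report the number of undetermined children per arm alongside, and update the time-to-event column of Table 2-4 for these two rows.

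Do not switch to a simple proportion over all FAS children. It counts every lost child as a non-failure and understates failure by more than the present rule overstates it (18.4% against 20.4% for a true 20%, with 10% evenly spread loss). If it is shown, label it a lower bound. If the present proportion is kept as a supplementary display, name its denominator as a subset of the FAS.

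The cost is a wording change in the SAP and one table program. No new data are needed.

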2.7.2.4 Parasite clearance time (PCT) and fever clearance time (FCT)

Descriptive statistics (mean, standard error, median, quartiles) will be presented using the Kaplan-Meier method. Kaplan-Meier curves will be provided.

PCT will be calculated based on uncorrected asexual parasite counts. Patients without parasite clearance for whatever reason will be censored at the time of last parasite assessment. Patients who were enrolled on the basis of history of fever and did not subsequently have a fever at pre-dose will not be included in the analysis of FCT. Patients without fever clearance for whatever reason will be censored at the time of last temperature assessment. Patients who received any antimalarial medication (including rescue medication) before (parasite or fever) clearance will be censored at the first use of antimalarial medication. If the study medication is vomited in the same date as the use of antimalarial medication, the last vomiting time on the study medication date is imputed as time of antimalarial medication. Otherwise, the antimalarial medication time can be imputed using the middle day time (12:00). The between treatment difference will be evaluated exploratorily using a log-rank test separately by cohort and stratified by cohort for pooling Cohorts 1 and 2 if cohort 2 does not stop early; otherwise log-rank test will be performed for Cohorts 1 and 2 separately.

Additional analysis for FCT will be performed by excluding patients who took anti-pyretic drugs (ATC2 code as N02 or M01) prior to FCT.

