Population	The study population will consist of male and female patients (Run-in Cohort: 12 to < 18 years old and ≥ 35.0 kg; Cohort 1: 2 to < 12 years old and ≥ 10.0 kg; Cohort 2: 6 months to < 2 years old, weight ≥ 5.0 kg) with confirmed uncomplicated P. falciparum malaria. In the Run-In Cohort, patients will have malaria symptoms and P. falciparum counts of ≥ 1,000 and ≤ 150,000 parasites/μL at pre-screening. In Cohort 1 and Cohort 2, patients will have malaria symptoms and P. falciparum counts of ≥ 1,500 and ≤ 150,000 parasites/μL at pre-screening.

Key Inclusion criteria	
 
• In Run-in Cohort: Male and female patients 12 to < 18 years of age, with a body weight <math>\geq 35.0</math> kg; In Cohort 1: Male and female patients 2 to < 12 years of age, with a body weight <math>\geq 10.0</math> kg; In Cohort 2: Male and female patients 6 months to < 2 years of age, with a body weight <math>\geq 5.0</math> kg
 
• Microscopic confirmation of P. falciparum by Giemsa-stained thick and thin films
 
• P. falciparum parasitemia of <math>\geq 1,000</math> and <math>\leq 150,000</math> parasites/<math>\mu</math>L at the time of pre-screening for Run-in Cohort
 
• P. falciparum parasitemia of <math>\geq 1,500</math> and <math>\leq 150,000</math> parasites/<math>\mu</math>L at the time of pre-screening for Cohorts 1 and 2
 
• Axillary temperature <math>\geq 37.5</math> °C or oral/tympanic/rectal temperature <math>\geq 38.0</math> °C; or history of fever during the previous 24 hours (at least documented verbally)
 
• Written informed consent has been obtained from parent / legal guardian before any assessment is performed. If the parent / legal guardian is unable to read and write, then a witnessed consent according to local ethical standards is permitted. Patients who are capable of providing assent, must provide assent with parental/legal guardian consent or as per local ethical guidelines
 
• The patient and his/her parent/legal guardian is able to understand and comply with protocol requirements, instructions and protocol-stated restrictions and is likely to complete the study as planned.
 

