#### Cohorts 1 and 2:

Approximately 220 (up to 268 in case Cohort 2 stops early and additional patients are enrolled in Cohort 1) male and female pediatric patients (6 months to < 12 years old) will be randomized to the study. There will be two sequential age-descending cohorts of approximately 140 patients for Cohort 1 and 80 patients for Cohort 2: Cohort 1 will include children 2 to < 12 years and Cohort 2 will include children 6 months to < 2 years (Figure 3-1 and Figure 3-2). In the event that Cohort 2 is stopped early, such as after the first 24 patients, 80 additional patients will be enrolled in Cohort 1. Randomization will be stratified by age group (6 years to < 12 and 2 to < 6 years) and country for Cohort 1, and by country for Cohort 2. Children will have a body weight  $\geq 10$  kg in Cohort 1 and  $\geq 5$  kg in Cohort 2.

The Screening Period for the three cohorts will consist of two visits: a Pre-Screening visit and a Screening visit.

- **Pre-Screening visit:** Pre-screening is a key element to successfully identify the right patients to be screened for this clinical study. During pre-screening, a *P. falciparum* parasite count will be obtained. Patients in the Run-in cohort should have a *P. falciparum* parasitemia of  $\geq 1,000$  and  $\leq 150,000$  parasites/ $\mu$ L at the time of the pre-screening visit to be further screened. Patients Cohort 1 and Cohort 2 should have a *P. falciparum* parasitemia of  $\geq 1,500$  and  $\leq 150,000$  parasites/ $\mu$ L at the time of the pre-screening visit to be further screened.
- **Screening visit:** Further screening assessments will take place as soon as the pre-screening *P. falciparum* parasitemia outcome is available and only if outcome is in the pre-defined range ( $\geq 1,000$  and  $\leq 150,000$  parasites/ $\mu$ L in Run-In Cohort and  $\geq 1,500$  and  $\leq 150,000$  parasites/ $\mu$ L in Cohort 1 and Cohort 2 ).

It is not permissible to re-screen a patient within the same malaria episode if s/he fails the initial pre-screening or screening. Re-screening of a patient may occur in case the patient is returning to the study site for a new malaria episode. In this case, the patient will be assigned a new study number.

All eligible patients will be admitted to the hospital on Day 1. Another *P. falciparum* parasite count will be obtained prior to dosing on Day 1. The outcome of the Day 1 visit parasite count will be used as the baseline count.

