### **PCT and FCT:**

Descriptive statistics (mean, standard error, median, quartiles) will be presented using the Kaplan-Meier method. Kaplan-Meier curves will be provided.

PCT will be calculated based on uncorrected parasite counts. Patients without parasite clearance for whatever reason will be censored at the time of last parasite assessment. Patients who were enrolled on the basis of history of fever and did not subsequently have a fever at pre-dose will not be included in the analysis of FCT. Patients without fever clearance for whatever reason will be censored at the time of last temperature assessment.

For Cohorts 1 and 2 pooled, the treatment difference between KAF156 and LUM-SDF and Coartem® will be evaluated at the 2-sided 5% significance level using a log-rank test stratified by cohort. For each cohort, the treatment difference between 2 treatment groups will be evaluated at the 2-sided 5% significance level using a log-rank test.

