2.3.2 Patient demographics and other baseline characteristics

Demographic data and baseline disease characteristics will be descriptively presented and tabulated per treatment group, as well as overall, using FAS and PPS. If there are patients in the SAF excluded from FAS, summary will also be provided for the SAF.

Following demographic variables will be summarized

- Age and age categories (6 months to < 2 yrs, 2 to <6 yrs, 6 to <12 yrs, 12 to <18 yrs)
- Sex (male, female)
- Race (White, black, Asian, native American, pacific islander, unknown, other)
- Ethnicity
- Body weight and weight categories (5 to <10, 10 to <15, 15 to <25, 25 to <35, 35 to <55, 55 to <75, and ≥ 75 kg)
- Body height (cm)
- BMI and BMI categories (<16, 16 to 25, >25) (Kg/m²)

Following disease characteristics at baseline will be summarized

- Body temperature and categories equivalent to axillary method (<37.5, 37.5 to <38.5, ≥ 38.5) (°C)
- Falciparum species: (P. Falciparum asexual forms, [REDACTED], P. Vivax, P. Ovale, P. malariae, P. Knowlesi, and Mixed-infection, n (%))
- P. falciparum density per micro ltr. and its categories (<1,000, 1,000 to <2,000, 2,000 to <5,000, 5,000 to <15,000, 15,000 to <50,000, 50,000 to <100,000, 100,000 to <150,000, $\geq 150,000$ parasites/ μ L; <100,000 / μ L, $\geq 100,000$ parasites / μ L)

[REDACTED]

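### The exploratory comparison of parasite clearance time is valid but inefficient: it is stratified by cohort only and makes no use of the Day 1 parasite density that the trial already collects

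*SAP*

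**What the plan says.** SAP 2.7.1 defines PCT as "time from the first dose until the first total and continued disappearance of (*P. Falciparum*) asexual parasite forms", sustained for a further 48 hours, and analyses it in the FAS. SAP 2.7.2.4 sets the arm comparison: "The between treatment difference will be evaluated exploratorily using a log-rank test separately by cohort and stratified by cohort for pooling Cohorts 1 and 2". Protocol 12.5.1 says that the pooled difference "will be evaluated at the 2-sided 5% significance level using a log-rank test stratified by cohort", with an unstratified log-rank test within each cohort.

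On density, the protocol summary requires "counts of ≥ 1,500 and ≤ 150,000" parasites/µL at pre-screening in Cohorts 1 and 2. A separate, later count serves as baseline: "The outcome of the Day 1 visit parasite count will be used as the baseline count" (protocol section 3). SAP 2.3.2 tabulates "P. falciparum density per micro ltr. and its categories" by treatment group, with boundaries that include 5,000, 15,000 and 50,000/µL.

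Density plays no part in the PCT comparison:
- Allocation: "Randomization will be stratified by age group (6 years to < 12 and 2 to < 6 years) and country for Cohort 1". Cohort 2 uses country only.
- Pooled analyses: SAP 2.1 uses cohort as the only stratum. It leaves out country and age because of small numbers per category.
- PCT subgroups: SAP 2.7.2.7 lists age, weight and sex.

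SAP 2.7.2 describes the secondary endpoints as supportive, with no pre-specified hypotheses and no multiplicity adjustment.

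**The concern.** PCT ends when no asexual parasites are seen. A child who starts with more parasites takes longer to reach that point at the same rate of clearance. Starting load is therefore likely to drive part of the spread in PCT, and a test that ignores it counts that spread as noise.

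Two things follow. The test is less likely to detect a real difference in clearance rate. And since density is not a randomisation stratum, a chance difference in density between arms passes into the PCT result. What is at stake is the precision and readability of one named secondary endpoint. If an imbalance appears after database lock, an adjustment chosen then will carry less weight than one written down beforehand.

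**Working it through.** **The plan's own figure.** The documents state no power, effect size or event count for PCT. The only related figure is the primary power: Φ(0.10/√(2×0.95×0.05/92) − 1.96) = Φ(3.11 − 1.96) = 87.5%, against at least 87% stated. Then 92/0.84 = 109.5, so 110 per arm and 220 in all. These 220 children (about 70 + 40 per arm by cohort) are used below.

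**How density enters PCT (assumption: log-linear clearance).** PCT = ln(P₀/L)/k, with starting density P₀, detection limit L and clearance rate k. The entry range is 150,000/1,500 = 100-fold. With k = 0.22/h and L = 40/µL (both assumed), PCT is ln(37.5)/0.22 = 16.5 h at the lower limit and ln(3,750)/0.22 = 37.4 h at the upper. A 10% faster rate shortens these by only 1.5 h and 3.4 h.

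**Chance imbalance.** Assume density is log-uniform over the entry range. The SD of ln density is ln(100)/√12 = 1.33, and the SD of the difference in arm means is 1.33×√(2/n).

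| Set | n per arm | SD of difference | 95% limit, ratio of geometric means | Chance of ratio beyond 1.25 either way |
|---|---|---|---|---|
| Pooled | 110 | 0.179 | e^(1.96×0.179) = 1.42 | 21% |
| Cohort 1 | 70 | 0.225 | 1.55 | 32% |
| Cohort 2 | 40 | 0.297 | 1.79 | 45% |

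**Power, model A.** Rate 0.22/h, detection limit 40/µL, films at 6, 12, 24, 36, 48, 72 and 96 h, 1,500 runs per setting. Density is log-uniform or narrower (log-normal, SD 1.0, truncated to the entry range). The density strata are cut at 5,000, 15,000, 50,000 and 100,000/µL within cohort.

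| Density | CV of clearance rate | Rate ratio | Planned test | Density-stratified | Gain (points) |
|---|---|---|---|---|---|
| Log-uniform | 20% | 1.10 | 52.9% | 76.4% | 23.5 |
| Log-uniform | 30% | 1.13 | 58.6% | 73.4% | 14.8 |
| Log-uniform | 50% | 1.20 | 66.8% | 70.9% | 4.1 |
| Narrower | 20% | 1.10 | 66.5% | 78.9% | 12.4 |
| Narrower | 30% | 1.13 | 66.7% | 73.6% | 6.9 |
| Narrower | 50% | 1.20 | 69.7% | 70.9% | 1.2 |

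Across these settings, density explains about 10% to 56% of the variance of ln PCT.

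**Power, model B.** Half-life log-normal about 2.5 h, detection limit 10/µL, four density groups cut at 5,000, 15,000 and 50,000/µL.
- Log-uniform density, log-SD 0.25: 53.9% to 66.2% (half-life ratio 1.10) and 84.9% to 93.4% (1.15).
- Log-uniform density, log-SD 0.35: 37.6% to 41.3% and 64.4% to 72.8%.
- Narrower density, ratio 1.10, 800 runs: 59.0% to 63.8% (log-SD 0.25), 41.0% to 42.1% (0.35) and 25.2% to 24.9% (0.50).

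**Small sets, model B.** For Cohort 2 alone (40 per arm, ratio 1.10), power goes from 19.1% to 18.5% with narrower density and log-SD 0.35. It gains 4 points with log-uniform density and log-SD 0.25. At 12 per arm the change is about +1 to −2 points, within simulation error.

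**No treatment effect.** The planned test rejects in 4.3% to 5.8% of runs in model A and 4.7% to 5.1% in model B. The stratified test rejects in 4.1% to 5.4% and 4.5% to 5.9%. In model A, the planned z statistic correlates −0.30 to −0.68 with the density imbalance. In the 10% most imbalanced trials (150 per setting, so a rough figure) its false-positive rate is about 7% to 25%.

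**The case against.** The strongest reply is that nothing here is an error. The log-rank test is valid under randomisation, the SAP calls the comparison exploratory, and no decision rests on its p-value. An imbalance would also be visible in the baseline table. All of this stands, and it limits the point to efficiency and to how the test behaves in an imbalanced sample.

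The size of the gain also rests on outside assumptions. The documents give no relation between density and PCT, no clearance rate and no detection limit. Log-uniform density favours adjustment, and with narrower density and widely varying clearance rates the gain disappears. This stands too, so only a range can be given.

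SAP 2.1 declines finer strata because of small samples. That reason concerns country and age. Eight cohort-by-density strata for 220 children average 27.5 each, which is workable. Four strata among 24 patients average 6, or 3 per arm, and there the objection holds.

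A reader might infer that the analysed baseline spans 100-fold by design. The documents do not support that. The limits apply at pre-screening, the baseline is the later Day 1 count, the FAS requires only a count above zero, and the SAP categories begin below 1,000/µL. A lowest stratum starting at 1,500/µL would leave some FAS children without a stratum, and 1,500 is not a boundary in SAP 2.3.2.

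A reader might also extend the point to fever clearance time and baseline temperature. No calculation supports this. That analysis already excludes children without pre-dose fever and has an added analysis without antipyretic users.

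**Conclusion.** The point holds as a cheap improvement of minor severity. The PCT comparison is valid but leaves out a baseline value that is collected, categorised and, under log-linear clearance, prognostic. Using it would add about 0 to 24 points of power in the pooled set and would reduce, though not remove, the effect of chance imbalance. The gain is largest when density is widely spread and clearance rates are similar between children, and close to nil when clearance rates vary widely.

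It would be wrong to read this as an inflated type I error, since the overall rate is about 5% with either test. Nor does it reach the primary non-inferiority conclusion, which concerns PCR-corrected ACPR at Day 29 and does not use PCT.

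**What to change.** In SAP 2.7.2.4, for pooled Cohorts 1 and 2 (or Cohort 1 alone if Cohort 2 stops early), pre-specify one PCT comparison adjusted for Day 1 baseline density. Choose one of these in advance:
- a log-rank test stratified by cohort and density group: below 5,000; 5,000 to <15,000; 15,000 to <50,000; 50,000/µL or more. The cuts are boundaries in SAP 2.3.2, and the open-ended lowest group gives every FAS child a stratum;
- a Cox model stratified by cohort, with log10 baseline density as covariate and a stated method for ties, since films are read at fixed times.

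If Cohort 1 is analysed alone, the cohort stratum drops out. Report the result beside the cohort-stratified log-rank test of protocol 12.5.1, which stays as planned, and record the addition in SAP section 4, which currently lists no changes. State that density strata are not used in small sets such as 24 patients. Leave the fever clearance analysis as it is.

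The cost is one extra analysis and some sparse strata that contribute little. No new data are needed, and FAS membership already requires a baseline count. The text should be final before database lock.
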